5.1 Phase I Dose Escalation Study

The phase I study includes three dose levels. Each cycle is 28 days. Patients will continue to receive therapy until progressive disease, unacceptable toxicity, or if any other withdrawal criteria are met.

Dose level	Romidepsin	Ixazomib
4 (start)	10mg/m ² IV on days 1, 8, 15	4 mg PO on days 1, 8, 15
5	14mg/m ² IV on days 1, 8	4 mg PO on days 1, 8, 15
6	14mg/m ² IV on days 1, 8, 15	4 mg PO on days 1, 8, 15

Dose assignments during phase 1 will be made according to the TITE-CRM design⁸². The first patient enrolled will be assigned to dose level 4. Subsequent patients will be assigned to a dose level based on the estimated probability of DLT (as determined by a statistical model; see Section 12.1 for details). Each patient will be assigned to a dose level as he/she is enrolled (based on the information available at the time). A new patient does not have to wait for previous patients to complete the first cycle before being assigned to a dose level. However, to ensure safety, no patient will be assigned to dose level 5 or 6 until at least one patient has completed the first cycle at dose level 4 with no DLTs.

Enrollment will continue until either (i) 18 patients have been treated at one dose level, and the next enrolled patient would also be assigned to that dose level, or (ii) a total of 36 patients have been enrolled across all dose levels combined.

The estimated MTD is the dose level with a model-estimated rate of DLT closest to 25% (but not more than 33%) after 36 patients have been enrolled (or the dose level where 18 patients have been treated, and the next enrolled patient would also be assigned to that dose level).

NOTE: After the first six patients have completed the first cycle, if the estimated rate of DLT at dose level 4 exceeds 0.33, the trial will stop for toxicity.

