5.6 Supportive Care

5.6.1 Romidepsin

Treatment with romidepsin has led to myelosuppression, infections, electrocardiographic changes, and tumor lysis syndrome. Management regarding these events is outlined below and please refer to standard guidelines for management.

Myelosuppression

Treatment can cause thrombocytopenia, leukopenia (neutropenia and lymphopenia), and anemia. Monitor blood counts regularly during treatment with romidepsin, and modify the dose as described in Section 6.2.

Electrocardiographic Changes

Several treatment-emergent morphological changes in EKGs (including T-wave and ST-segment changes) have been reported in clinical studies. The clinical significance of these changes is unknown. In patients with congenital long QT syndrome, patients with a history of significant cardiovascular disease, and patients taking anti-arrhythmic medicines or medicinal products that lead to significant QT prolongation, consider cardiovascular monitoring of EKGs at baseline and periodically during treatment. Confirm that potassium and magnesium levels are within normal range before administration of romidepsin.

Tumor Lysis Syndrome

In patients with Stage III/IV disease and/or high tumor burden are at greater risk for tumor lysis syndrome and should be closely monitored, and managed as per standard guidelines.

Nausea and/or Vomiting

Antiemetics: prefer that non-5-HT₃ serotonin receptor antagonists be used at the discretion of the investigator. The dose and regimen will be according to institutional guidelines. If 5-HT₃ serotonin receptor antagonists are required for to nausea refractory to initial agents, then monitoring the QT interval is necessary with periodic EKGs.

Fluid deficits should be corrected before initiation of study drug and during treatment.

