6.2 Dose Modifications

Dose modifications below are outlined for the Phase I portion of the trial. Further information on the Phase II dose modification will be determined after the MTD is established.

Treatment with romidepsin and ixazomib will use a cycle length of 28 days. Missed doses within a cycle will not be made up. For example, if drug is held on Day 8 and given the next week, the day of administration will be Day 15; Day 8 will be considered as missed. Once a dose of romidepsin or ixazomib is reduced, the dose may only be re-escalated after discussion with and approval by the sponsor investigator. If a delay occurs on day 1 of a cycle, then day 1 will be when the first dose of a cycle is given.

For a new cycle of treatment to begin or resumption of treatment within a cycle, the patient must meet the following criteria:

- ANC $\geq 1,000/\text{mm}^3$.
- Platelet count $\geq 75,000/\text{mm}^3$.
- Concurrent magnesium and potassium supplementation is allowed to maintain levels within a normal range.
- All other nonhematologic toxicity (except for alopecia) must have resolved to \leq Grade 1 or to the patient's baseline condition.

Hematologic toxicities:

Toxicity	Action
Within-Cycle (day 8 and 15) Dose Modifications 
 • If platelet count $< 30 \times 10^9/\text{L}$ or ANC $< 0.50 \times 10^9/\text{L}$ on treatment days 8 and 15 (for dose adjustments on day 1, see below). 	
 • Hold treatment • Obtain CBC with diff 2x/week until platelet count or ANC have reached goal outlined above • Upon recovery, reinitiate treatment at 1 dose level reduction as per section 6.3.
Dose Modifications for Subsequent Treatment Cycles 
 • ANC $< 1.0 \times 10^9/\text{L}$, platelet count $< 75 \times 10^9/\text{L}$ on day 1 of a cycle. 	
 • Hold romidepsin and ixazomib until resolution as per criteria above • Obtain CBC with diff 2x/week until platelet count or ANC have reached goal outlined above • Upon recovery, reinitiate treatment at 1 dose level reduction as per section 6.3. • The maximum delay before treatment may be discontinued is 21 days and at the discretion of the local PI.

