
 • Delay of > 2 weeks in the start of a subsequent cycle due inadequate recovery to goals outlined above. 	
 • Hold romidepsin and ixazomib until resolution as per criteria above • Obtain CBC with diff 2x/week until platelet count or ANC have reached goal outlined above

Toxicity	Action
	
 Upon recovery, reinitiate treatment at 1 dose level reduction as per section 6.3. The maximum delay before treatment may be discontinued is 21 days and at the discretion of the local PI.

 Grade 4 febrile neutropenia or thrombocytopenia 	
 Hold treatment Obtain CBC with diff 2x/week until platelet count or ANC have reached goal outlined above Upon recovery, reinitiate treatment at 1 dose level reduction as per section 6.3.

Non-Hematological Toxicity Dose Reductions Related to Study Drugs (except alopecia)

NCI CTCAE Grade	Romidepsin	Ixazomib
0-1	No change	No change
2-3	Hold until resolved to \leq Grade 1, then resume at same level	Hold until resolved to \leq Grade 1, then resume at same level with exceptions as outlined in table “Non-hematological Toxicity Dose Reductions specific to Ixazomib”
Second episode of grade 3 OR First episode 4 toxicity	Hold until resolved to \leq Grade 1, then resume at 1 dose level reduction as per section 6.3.	Hold until resolved to \leq Grade 1, then resume at 1 dose level reduction as per section 6.3.
Third episode of grade 3 OR Second episode 4 toxicity	Hold until resolved to \leq Grade 1, then resume at 1 dose level reduction as per section 6.3. If toxicity occurs at lowest dose level, then treatment should be discontinued	Hold until resolved to \leq Grade 1, then resume at 1 dose level reduction as per section 6.3 or discontinue based on local PI judgement If toxicity occurs at lowest dose level, then treatment should be discontinued

Non-hematological Toxicity Dose Reductions specific to Ixazomib:

Peripheral Neuropathy	

 New or worsening Grade 1 peripheral neuropathy with pain or Grade 2 	
 Hold study drug until resolution to Grade \leq 1 or baseline

 New or worsening Grade 2 peripheral neuropathy with pain or Grade 3 	
 Hold study drug until resolution to Grade \leq 1 or baseline Reduce study drug to next lower dose upon recovery

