6.3 Dose Levels for Dose Reductions for Phase I

Dose level	Romidepsin	Ixazomib
6	14 mg/m ² D 1, 8, 15	4mg D 1, 8, 15
5	14 mg/m ² D 1, 8	4mg D 1, 8, 15
4 (Starting dose)	10 mg/m ² D 1, 8, 15	4mg D 1, 8, 15
3	10 mg/m ² D 1, 8, 15	3mg D 1, 8, 15
2	10 mg/m ² D 1, 8, 15	3mg D 1, 8
1	10 mg/m ² D 1, 8, 15	2.3mg D 1, 8
0	Discontinue	Discontinue

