7.2 On Treatment Evaluations

7.2.1 Cycle 1+, Day 1

- Laboratory assessments: CBC, CMP, Mg, LDH
 - **Note:** Cycle 1 Day 1 lab testing need not be repeated if completed within 7 days of starting protocol therapy.
- Correlative laboratory assessments: see section 7.2.3
- Office visit
- Physical Exam with vital signs and weight
- ECOG performance status
- Adverse event (AE) assessment

- Concomitant medication review
- Drug administration of romidepsin and ixazomib per dosing cohort

7.2.2 Cycle 1+, Day 8 and 15

- Laboratory assessment: CBC, CMP, Mg, LDH for first 3 cycles.
- Drug administration of romidepsin and ixazomib per dosing cohort

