12.3 Sample Size and Accrual

The maximum sample size across both phases will be 48: up to 36 in phase I and 12 additional patients in phase II. Table 12.3.1 provides justification for the phase I sample size. In simulations of eight different dose-toxicity curves, the phase I study identified an acceptable dose level, defined as having true rate of DLT within 0.25 ± 0.08 , with probability between 0.56-0.83 (assuming that at least one

such dose level exists). This probability increases if more than one dose level is considered acceptable or if the true rates of DLT differ more between dose levels.

Table 12.3.1: Phase I Operating Characteristics from 1000 simulated trials. Up to 36 patients are enrolled (unless 18 patients are enrolled to estimated MTD)

True DLT Rates (3 Dose Levels; Acceptable* in Bold)	% Trials Estimating Acceptable Dose as MTD	% Trials Stopping for Toxicity	% Trials Enrolling < 18 at Estimated MTD	# Patients Enrolled to Estimated MTD: 5 th Percentile	Total # Patients Enrolled: (5 th , 95 th) Percentile
{0.10,0.11, 0.33 }	63%	0.3%	12.8%	15	(22,36)
{0.10,0.15, 0.20 }	77%	0.4%	5.4%	17	(22,36)
{0.13, 0.30,0.32 }	83%	0.7%	7.6%	17	(21,36)
{0.15, 0.18,0.37 }	56%	2.2%	11.5%	15	(21,36)
{0.15, 0.25,0.52 }	76%	1.8%	7.7%	16	(21,36)
{ 0.20,0.23 ,0.39}	75%	4.6%	7.4%	17	(19,36)
{ 0.26,0.33 ,0.43}	80%	14.1%	6.9%	17	(19,36)
{0.36,0.45,0.57}	--	46.2%	5.2%	17	(19,36)

*Acceptable dose levels have true rates of DLT within 0.25 +/- 0.08

Table 12.3.2 provides justification for the phase II sample size of 12 additional patients. The phase II stage will power at least 0.80 to detect a CR rate at the estimated MTD of 0.35, as long as at least 16 patients from phase I are at the estimated MTD, which would yield a total sample size of 28.

Table 12.3.2: Phase II Operating Characteristics from 1000 simulated trials. Up to 30 patients are enrolled. The futility analysis proceeds if at least 3 patients demonstrate CR, and the MTD is found to be efficacious at the final analysis if at least 8 patients demonstrate CR.

True CR rate at MTD	# Patients to MTD in Phase I (+Phase II)	% Trials Stopping for Futility	% Trials Finding MTD to be Inefficacious	% Trials Finding MTD to be Efficacious (Type I error – Power)
0.15	18(+12)	48%	45%	6.8%
0.15	17(+12)	52%	42%	5.7%
0.15	16(+12)	56%	39%	4.7%
0.25	18(+12)	14%	39%	48%
0.25	17(+12)	16%	40%	44%
0.25	16(+12)	20%	41%	39%
0.35	18(+12)	2.4%	11%	87%
0.35	17(+12)	3.3%	12%	84%
0.35	16(+12)	4.5%	15%	81%

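### From cycle 4 the Day 8/15 hold rule and electrolyte check rely on labs that are not scheduled, and a one-level reduction from level 5 raises planned romidepsin per cycle

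*Combined protocol and SAP*

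**What the plan says.** **Hold rule and labs.** The within-cycle rule in Section 6.2 holds treatment if platelets are below 30 or ANC below 0.50 x 10⁹/L "on treatment days 8 and 15 (for dose adjustments on day 1, see below". It names no cycle limit. Section 5.6.1, under electrocardiographic changes, adds: "Confirm that potassium and magnesium levels are within normal range before administration of romidepsin". Section 7.2.2, which covers Days 8 and 15 from cycle 1 onward, lists drug administration without a limit, but the labs as "Laboratory assessment: CBC, CMP, Mg, LDH for first 3 cycles". The calendar marks the same labs C1-3, and footnote 10 confirms it. Section 5.1 continues treatment until progression, unacceptable toxicity or withdrawal.

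**Reduction rule.** For hematologic toxicity Section 6.2 says to "reinitiate treatment at 1 dose level reduction as per section 6.3"; for repeated or grade 4 non-hematologic toxicity it says "resume at 1 dose level reduction as per section 6.3". In Section 5.1 level 5 gives romidepsin "14mg/m ² IV on days 1, 8", and calendar footnote 16 confirms that level 5 has no Day 15 romidepsin. One row below it in Section 6.3 is the row marked "4 (Starting dose", with romidepsin 10 mg/m² on Days 1, 8 and 15. Ixazomib is 4 mg on Days 1, 8 and 15 at both levels. Section 6.2 limits these rules to Phase I and leaves the Phase II rules until the MTD is known.

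**Simulations.** Section 12.3 reports that an acceptable dose is found "with probability between 0.56-0.83" over eight dose-toxicity curves, provided that an acceptable level exists.

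**The concern.** A rule that acts on a Day 8 or Day 15 blood count needs that count. If the schedule stops asking for it after cycle 3 while dosing goes on, sites must decide for themselves whether to draw it, and holds in later cycles will depend on local habit. The same applies to the electrolyte check.

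The level table raises a related question. A patient who steps down for toxicity would be expected to receive less of the drug. If the planned cycle total goes up instead, the word reduction does not say what is being reduced. Level 5 is not a corner case: it is an acceptable dose in five of the eight rows of Table 12.3.1. The same table also prompts the question of whether the dose-finding results depend on level 5 being more toxic than level 4.

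**Working it through.** **1. Labs against dosing.** Inputs: Sections 5.1, 5.6.1, 6.2, 6.3 and 7.2, calendar footnotes 9, 10 and 16.

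| | Cycles 1-3 | Cycle 4 onward |
|---|---|---|
| At least one study drug on Days 1, 8 and 15 | yes | yes |
| Day 1 CBC, CMP, Mg scheduled | yes | yes |
| Day 8/15 CBC, CMP, Mg scheduled | 2 per cycle | 0 per cycle |
| Within-cycle hold in 6.2 applies | yes | yes |

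The first row holds at every level in Section 6.3: level 5 omits Day 15 romidepsin but keeps Day 15 ixazomib, and levels 1 and 2 do the reverse. Potassium is part of the CMP (footnote 9), so it drops out with the CBC. Two of three treatment days per cycle therefore have no scheduled labs from cycle 4. Cycles that late are expected, since imaging is planned before cycle 5 and every three cycles after that.

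**2. Planned dose per cycle.** The documents give no per-cycle total to reproduce. Formula: dose per administration x administrations per 28-day cycle, from the table in Section 6.3.

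| Level | Romidepsin (mg/m²) | Ixazomib (mg) |
|---|---|---|
| 6 | 14 x 3 = 42 | 4 x 3 = 12 |
| 5 | 14 x 2 = 28 | 4 x 3 = 12 |
| 4 | 10 x 3 = 30 | 4 x 3 = 12 |
| 3 | 10 x 3 = 30 | 3 x 3 = 9 |
| 2 | 10 x 3 = 30 | 3 x 2 = 6 |
| 1 | 10 x 3 = 30 | 2.3 x 2 = 4.6 |

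- Step 6 to 5: (28 - 42)/42 = -33.3% romidepsin.
- Step 5 to 4: (30 - 28)/28 = +7.1% romidepsin, ixazomib unchanged, infusions from 2 to 3. Dose per infusion: (10 - 14)/14 = -28.6%.
- Cumulative romidepsin after Days 1, 8 and 15: level 5 is 14, 28, 28; level 4 is 10, 20, 30. Level 4 is lower until Day 15 and higher after it.
- Levels 4 to 1 all total 30, so no lower level has a planned romidepsin total below the 28 of level 5.

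**3. Level order in the simulations.** The model in Section 12.1 raises the skeleton values 0.05, 0.15 and 0.27 to the power exp(b). Since exp(b) is positive, level 5 is modelled as more toxic than level 4 for every b. All eight curves in Table 12.3.1 have the same order; the closest pair is 0.10 and 0.11.

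The protocol states no prior for b. With an assumed prior SD of 0.6 and 2 patients per month, a re-simulation comes close to the published rows:

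| Curve | Acceptable, re-run (published) | Toxicity stop, re-run (published) |
|---|---|---|
| 0.15/0.25/0.52 | 75.9% (76%) | - |
| 0.20/0.23/0.39 | 74.8% (75%) | 4.6% (4.6%) |
| 0.26/0.33/0.43 | 81.0% (80%) | 13.4% (14.1%) |
| 0.36/0.45/0.57 | - | 46.1% (46.2%) |

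With the same assumptions and level 5 at or below level 4 (ranges are across separate runs of 500 to 1500 trials):

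| True DLT rates, levels 4/5/6 | Acceptable dose chosen |
|---|---|
| 0.20/0.20/0.40 | 70-73% |
| 0.22/0.20/0.40 | 70% |
| 0.25/0.23/0.40 | 75% |
| 0.30/0.28/0.45 | 72% |
| 0.30/0.25/0.45 | 74% |
| 0.18/0.15/0.33 | 57% |
| 0.36/0.25/0.50 | 38-43% (toxicity stop 30-35%) |
| 0.40/0.30/0.50 | 25-28% (toxicity stop 46-50%) |

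The 57% comes from 500 trials, with simulation error √(0.57 x 0.43/500) = 2.2 points, so it sits at the lower edge of the range. With a prior SD of 1.16 the 0.36/0.25/0.50 curve gives 18% acceptable and 63% stopped, so these figures depend heavily on the assumed prior.

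**The case against.** **On the labs.** A reader might infer that the hold cannot be triggered after cycle 3. The documents do not support that. Day 1 counts continue and gate every cycle, Section 5.6.1 asks for regular blood counts during romidepsin, Section 5.6.2 allows additional testing by standard practice, and any Day 8/15 count so obtained would trigger the rule. What remains is the absence of scheduled counts. The general wording does not close that gap, because Section 5.6.2 refers to monitoring as the protocol outlines it and Section 6 refers to the calendar, which is the schedule that omits them. It is also true that DLTs are counted in cycle 1 only, so this gap does not affect the MTD estimate.

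**On the reduction.** The order 4, 5, 6 is used consistently in Sections 5.1, 6.3 and 12.1, reduction is never defined as a lower cycle total, and the dose per infusion does fall. Only the 5-to-4 step is affected, and only in Phase I as the rules stand. This is therefore a mismatch between a word and the totals that follow from the table, and not a direct contradiction.

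**On the simulations.** A reader might infer that 0.56-0.83 fails once level 5 is no more toxic than level 4. It does not: the equal and mildly inverted curves above stay within it. The large losses need level 5 to be 10 or 11 percentage points less toxic than level 4, which nothing in the documents suggests. In both of those curves level 4 itself exceeds the 0.33 limit, so many of the stops are the safety rule acting on a starting level that is too toxic. The range is also already tied to eight stated curves.

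**Conclusion.** The main point stands on the text alone. From cycle 4 the protocol schedules no Day 8/15 counts or electrolytes, although the hold rule and the electrolyte check have no cycle limit and dosing on those days continues. It concerns later-cycle safety and consistency between sites, not the MTD estimate.

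The secondary point stands by arithmetic: stepping from level 5 to level 4 raises planned romidepsin by 2 mg/m² per cycle (+7.1%) and adds a Day 15 infusion, while each infusion is smaller. It assumes full planned dosing and says nothing about which level is more toxic.

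The statistical point is only a possible sensitivity check. The stated 0.56-0.83 is not shown to be wrong; it is conditional on curves that share one order of levels. The re-simulated figures rest on an assumed prior SD and accrual pattern.

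**What to change.** 1. The clinical team must reconcile Sections 6.2 and 5.6.1 with Section 7.2.2 and calendar footnote 10, so that the rules and the lab schedule cover the same cycles. The cost is wording and, depending on how it is resolved, possibly blood draws at visits that already take place for dosing.
2. The clinical team must reconcile Section 6.2 with the level table in Sections 5.1 and 6.3, and state what reduction means for the step from level 5 to level 4. The same check belongs in the Phase II modification rules when they are written. The cost is wording. No dose, schedule or monitoring rule is proposed here.
3. Optional: note in Section 12.3 that all eight curves make level 5 more toxic than level 4, add an inverted curve to Table 12.3.1 as a sensitivity check, and state the prior for b. If the prior used cannot be recovered, give its SD as an assumption with a range. The cost is one simulation run.

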5.6.2 Ixazomib

Adverse drug reactions such as thrombocytopenia, diarrhea, fatigue, nausea, vomiting, and rash have been associated with ixazomib treatment. Management guidelines regarding these events are outlined below. Further details of management of ixazomib AEs are described in Section 6 of the Ixazomib IB.

Prophylaxis against Risk of Infection

If lymphopenia is noted, patients may be at an increased risk of infection. In particular, lymphopenia can be associated with reactivation of herpes zoster and herpes simplex viruses. Antiviral therapy such

as acyclovir or valacyclovir will be initiated as clinically indicated. Other antivirals are also acceptable, as clinically indicated.

Nausea and/or Vomiting

Antiemetics: prefer that non-5-HT₃ serotonin receptor antagonists be used at the discretion of the investigator. The dose and regimen will be according to institutional guidelines. If 5-HT₃ serotonin receptor antagonists are required for nausea refractory to initial agents, then monitoring the QT interval is necessary with periodic EKGs.

Fluid deficits should be corrected before initiation of study drug and during treatment.

Diarrhea

Diarrhea should be managed according to clinical practice, including the administration of antidiarrheals once infectious causes are excluded. Fluid intake should be maintained to avoid dehydration. Fluid deficits should be corrected before initiation of treatment and during treatment. Prophylactic antidiarrheals are not generally recommended.

Erythematous Rash With or Without Pruritus

As with VELCADE, rash with or without pruritus has been reported with ixazomib, primarily at the higher doses tested and when given with agents for which rash is an overlapping toxicity. The rash may range from some erythematous areas, macular and/or small papular bumps that may or may not be pruritic over a few areas of the body to a more generalized eruption that is predominately on the trunk or extremities. Rash has been most commonly characterized as maculopapular or macular. To date, when it does occur, rash is most commonly reported within the first 3 cycles of therapy. The first incidence of rash events occurred early during treatment, and there was no evidence of increased frequency of rash with prolonged exposure. The rash is often transient, self-limiting (resolves without medical intervention), and is typically Grade 1 to 2 in severity.

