Symptomatic measures such as oral or topical corticosteroids and/or antihistamines have been successfully used to manage rash and have been used prophylactically in subsequent cycles. The use of a topical, IV, or oral steroid (eg, prednisone ≤ 10 mg per day or equivalent) is permitted. Management of a Grade 3 rash may require IV antihistamines or corticosteroids. Administration of ixazomib (and/or other causative agents if given in combination) should be modified per protocol and re-initiated at a reduced dose level from where rash was noted.

In line with clinical practice, dermatology consult and biopsy of \geq Grade 3 rash or any SAE involving rash are recommended at the discretion of the investigator. Prophylactic measures should also be considered if a patient has previously developed a rash (eg, using a thick, alcohol-free emollient cream on dry areas of the body or oral or topical antihistamines). The rare risks of Stevens-Johnson syndrome, TEN, DRESS syndrome, and pemphigus vulgaris have been reported in oncology studies when ixazomib (or placebo) has been given in a multi-therapy regimen, with concomitant medications known to cause rash, and/or in the setting of confounding TEAEs. These severe, potentially life-threatening, or deadly conditions may involve rash with skin peeling and mouth sores and should be clinically managed according to standard medical practice. Study medications should be discontinued in the event of severe, potentially life-threatening rash.

Thrombocytopenia

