
 New or worsening Grade 4 peripheral neuropathy 	
 Discontinue study drug
Rash	

 Grade 2 	
 Symptomatic recommendations outlined in Section 5.4

Dosage in Patients with Hepatic Impairment

Reduce the starting dose of ixazomib to 3 mg in patients with moderate (total bilirubin greater than 1.5-3 x ULN) or severe (total bilirubin greater than 3 x ULN) hepatic impairment.

Dosage in Patients with Renal Impairment

Reduce the starting dose of ixazomib to 3 mg in patients with severe renal impairment (creatinine clearance less than 30 mL/min) or end-stage renal disease (ESRD) requiring dialysis. Ixazomib is not dialyzable and therefore can be administered without regard to the timing of dialysis.

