10.1.6 Adverse Events

The most common adverse events associated with ixazomib are thrombocytopenia, gastrointestinal toxicity (diarrhea, constipation, nausea, and emesis), peripheral neuropathy, peripheral edema, and cutaneous reactions. Please see package insert for the comprehensive list of adverse events.

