10.2.6 Adverse Events

The most likely adverse events from administration of romidepsin include fatigue, electrolyte disturbances, infections, sepsis, gastrointestinal toxicity (nausea, anorexia, vomiting, dysgeusia, diarrhea, and constipation), anemia, thrombocytopenia, neutropenia, and weakness. See package insert for the comprehensive list of adverse events.

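### Phase I, levels 6 and 5: for toxicity attributed to ixazomib, the reduction ordered in the section 6.2 ixazomib column can leave ixazomib at full dose, against the rash guidance in section 5.6.2

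*Combined protocol and SAP*

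**What the plan says.** Section 6.2 sets dose modifications for Phase I only. Its general non-hematologic table gives romidepsin and ixazomib a column each. In the ixazomib column:

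- Grade 2-3: hold until Grade 1 or less, "then resume at same level with exceptions as outlined in table", the table being the ixazomib-specific one that follows.
- Second Grade 3 or first Grade 4: hold, "then resume at 1 dose level reduction as per section 6.3".
- Third Grade 3 or second Grade 4: hold, "then resume at 1 dose level reduction as per section 6.3 or discontinue based on local PI judgement".

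Section 6.3 is the only ladder. Each of its levels is a romidepsin dose paired with an ixazomib dose.

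The ixazomib-specific table covers neuropathy, with its own rule that lowers the drug itself, and rash. The rash entry is for Grade 2 only: "Symptomatic recommendations outlined in Section 5.4". Section 5.4 is the drug administration section; the rash guidance is in section 5.6.2. There, directly after a sentence on managing Grade 3 rash, the protocol says: "Administration of ixazomib (and/or other causative agents if given in combination) should be modified per protocol and re-initiated at a reduced dose level".

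**The concern.** An instruction in a column headed ixazomib should change the ixazomib dose when ixazomib is held to be the cause. From levels 6 and 5, one step down section 6.3 changes romidepsin only. A patient with a recurrent Grade 3 event attributed to ixazomib can then be rechallenged with the same ixazomib dose, although a reduction has been ordered.

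Rash is the clearest example because the protocol itself says what should happen. Section 10.1.6 puts "peripheral neuropathy, peripheral edema, and cutaneous reactions" among the most common ixazomib events. Section 10.2.6 begins "The most likely adverse events from administration of romidepsin include fatigue, electrolyte disturbances, infections, sepsis, gastrointestinal toxicity", and its list does not include rash. Grade 4 rash is outside the example, since section 5.6.2 discontinues treatment for potentially life-threatening rash. Neuropathy is outside the point altogether. Diarrhea and fatigue are shared or romidepsin-listed events, and the joint ladder suits them unless the event is attributed to ixazomib.

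**Working it through.** The plan states no figure to reproduce. The check is planned dose times dosing days per 28-day cycle, using the doses in section 6.3.

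| Level | Romidepsin, mg/m2 per cycle | Ixazomib, mg per cycle |
|---|---|---|
| 6 | 14 x 3 = 42 | 4 x 3 = 12 |
| 5 | 14 x 2 = 28 | 4 x 3 = 12 |
| 4 | 10 x 3 = 30 | 4 x 3 = 12 |
| 3 | 10 x 3 = 30 | 3 x 3 = 9 |
| 2 | 10 x 3 = 30 | 3 x 2 = 6 |
| 1 | 10 x 3 = 30 | 2.3 x 2 = 4.6 |

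**The two reducing rows as written, read as joint levels** (assigned dose, then after each row):

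| Assigned level | Path | Ixazomib | Romidepsin | Steps leaving ixazomib unchanged |
|---|---|---|---|---|
| 6 | 6, 5, 4 | 12, 12, 12 | 42, 28, 30 | 2 |
| 5 | 5, 4, 3 | 12, 12, 9 | 28, 30, 30 | 1 |
| 4 | 4, 3, 2 | 12, 9, 6 | 30, 30, 30 | 0 |

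Unchanged steps: 2 + 1 + 0 = 3 of 6. Ixazomib first falls at level 3, which is three steps below level 6 and two below level 5. The step from 5 to 4 lowers neither drug's planned total per cycle (romidepsin 28 to 30), although the romidepsin infusion falls from 14 to 10 mg/m2.

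**Grade 3 rash.** The ixazomib-specific table has no Grade 3 row, so the general table applies.

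- First Grade 3 episode: section 6.2 resumes at the same level (12 mg from all three levels), while section 5.6.2 asks for a reduced one. This conflict does not depend on how a level is read, and it exists at level 4 too.
- Second episode: a step is ordered, but ixazomib stays at 12 mg from levels 6 and 5.
- Third episode: ixazomib stays at 12 mg from level 6 unless the local PI discontinues it.

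**With an ixazomib-specific step.** The two reducing rows give 12, 9, 6 mg from every level: 9/12 - 1 = -25% and 6/12 - 1 = -50%. With a Grade 3 rash row added, three rash episodes give 12, 9, 6, 4.6 mg. Romidepsin, under its own column, follows the same path as now.

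**The case against.** **The literal reading is not the only one.** The columns are separate, section 6.2 speaks of a dose of either drug being reduced, and section 5.4 gives ixazomib a range of 2.3-4 mg. A site could take the instruction to mean the next lower ixazomib dose. This stands: the documents permit that reading. But nothing defines the step from level 6 or 5, or says that romidepsin 14 mg/m2 may be paired with ixazomib 3 mg, so sites in a multicenter trial could dose the same event differently.

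**The joint ladder is a coherent design.** Phase I escalates romidepsin over a fixed ixazomib dose (section 12.1), and DLTs are judged against the combination (section 6.1), so stepping back first removes what escalation added. The ladder also works the other way: below level 4 romidepsin never falls. This stands for shared or uncertain attribution. It does not answer section 5.6.2, which explicitly asks for ixazomib to be restarted lower after rash.

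**The rash evidence is limited.** Section 5.6.2 says "rash with or without pruritus has been reported with ixazomib, primarily at the higher doses tested", but the sentence goes on to include use with agents that share rash as a toxicity. The same paragraph describes rash as usually Grade 1 to 2 and often transient. Section 1.3 presents 4 mg as the approved combination starting dose with acceptable safety. A reader might infer that 4 mg is shown to be too high for rash; the documents do not support that. Rash serves here only to show that two instructions disagree.

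**Safeguards exist.** These are the hold to Grade 1 or less, discontinuation by the local PI, treating-physician discretion (section 6.4) and weekly Phase I team meetings (section 13.1). They allow a pause, a stop or a discussion, but none specifies a lower ixazomib dose.

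**Sparing romidepsin is tempting but unsupported.** A reader might conclude that romidepsin should stay unchanged when ixazomib is blamed. The romidepsin column orders its own reduction for the same episodes, and both drugs are given on the same days. Holding romidepsin at 42 rather than 28 mg/m2 per cycle at level 6 on attribution alone would remove a protection the plan provides.

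**Conclusion.** The point holds as an internal conflict in the Phase I dosing rules. Read literally, 3 of the 6 ixazomib reductions ordered across levels 6, 5 and 4 leave ixazomib at 12 mg per cycle: both from level 6, the first from level 5, none from level 4. Separately, a first Grade 3 rash is returned to the same dose at every level, against section 5.6.2.

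This rests on three assumptions: a dose level means a joint row of section 6.3; the restart sentence in section 5.6.2 applies to Grade 3 rash, as its position suggests; and the doses are planned doses with none missed.

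The reach is narrow. Apart from first-episode Grade 3 rash, it concerns Phase I patients at level 6 or 5 with a recurrent Grade 3, or a Grade 4 other than rash, that is non-hematologic, not neuropathy and attributed to ixazomib. Three of six counts table steps; a reader might take it as a share of patients, but the documents give no event rate. Nor do they support inferring that lowering ixazomib is forbidden, or that the MTD estimate or CR rate is distorted. No such effect is claimed. The conflict should be corrected because patients could be re-exposed to full-dose ixazomib by following the tables as written.

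**What to change.** 1. State in section 6.2 that when the ixazomib column orders a reduction for toxicity attributed to ixazomib, ixazomib moves to its next lower dose in the section 6.3 ixazomib column: 4 mg D1,8,15, then 3 mg D1,8,15, then 3 mg D1,8, then 2.3 mg D1,8, then discontinue. State that the resulting pairs are allowed.
2. Leave romidepsin to its own column as now written. Do not require it to stay unchanged on attribution alone.
3. Add a Grade 3 rash row to the ixazomib-specific table: hold until Grade 1 or less, then resume at the next lower ixazomib dose. Point the rash entries to section 5.6.2.
4. Keep the joint ladder for shared or uncertain attribution and for hematologic toxicity, and leave the neuropathy rule as it is.

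The cost is an amendment and a site notice. No new procedure, ixazomib dose or capsule strength is needed. The price is some lost ixazomib dose intensity, including 9 instead of 12 mg per cycle after a first Grade 3 rash at any level, and more weight on attributing events between drugs given on the same days. A few pairs fall outside section 6.3. Tracing both columns from levels 6 and 5 gives three: romidepsin 14 mg/m2 x 3 with ixazomib 3 mg x 3, and romidepsin 14 mg/m2 x 2 with ixazomib 3 mg x 3 or 3 mg x 2. In each, ixazomib is below the assigned dose and within the section 5.4 range.
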